### **5.3 Visit 3 – Toxicity Assessment**

Initial safety and tolerability of the study drug will be assessed after 2 weeks on PD-0332991. The evaluation will include:

1. Clinical assessment – including interval history, physical examination, weight, vital signs, signs/symptoms, and performance status.
2. Toxicity assessment. Adverse events will be graded using the National Cancer Institute (NCI) Common Toxicity Terminology Criteria for Adverse Events v 4.0 (CTCAE v 4.0).
3. Concomitant medication review
4. Blood cell counts (CBC with differential, platelets) and comprehensive chemistries (albumin, alkaline phosphatase, total protein, BUN, creatinine, AST (SGOT), ALT (SGPT), total bilirubin, calcium, sodium, potassium, chloride, bicarbonate), lactate dehydrogenase (LDH).

If subject experiences a Grade 3 or greater toxicity deemed related to study drug, PD-0332991 will be temporarily discontinued. After the resolution of toxicity to Grade 2 or less, PD-0332991 will be restarted at the initial dose. The study treatment will be continued until disease progression or unacceptable side effects (Grade 3 or greater). Subjects with unacceptable side effects (Grade 3 or greater) for a second time on PD-0332991 will be removed from the study. The only exception to this are: Grade 3 anorexia, nausea vomiting, stomatitis/mucositis or diarrhea that will lead to investigational product withdrawal only if not manageable despite maximum supportive care.

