### **5.4 Subsequent visits on study – Response and Toxicity Assessment**

Safety and tolerability of the study drug will be assessed every 2 weeks after the initiation of PD-0332991 for the first 3 cycles of treatment, and every 4 weeks thereafter. Procedures will be as described for Visit 3. Additionally, Serum AFP will be monitored every 4 weeks and imaging will occur every 8 weeks after initiation of therapy to determine response of the disease to treatment. Subjects will undergo tumor response assessment per modification of RECIST (Version 1.1) guidelines. Radiological assessments must include CT of the chest, abdomen and pelvis and MRI of the liver. Magnetic Resonance Imaging is the preferred study for imaging the liver and must include T1, T2/flair and diffusion weighted imaging. Studies will be obtained at

baseline and according to schedule of observations until disease progression, death, withdrawal of consent, end of study or start of a new treatment. Unscheduled imaging may be conducted at the discretion of the Investigator.

Adverse events are defined in section 9.0. The investigator is responsible for reviewing all laboratory and clinical data, determining clinical significance and assessment of adverse events. It will be left to the investigator's clinical judgment to determine whether an adverse event is related and of sufficient severity to require subject's removal from treatment or from the study. The subject may also withdraw voluntarily from treatment due to what he/she perceives as an intolerable adverse event. If this arises the subject will be observed with extra visits until symptoms cease or the condition becomes stable. Adverse events will be graded using the National Cancer Institute (NCI) Common Toxicity Terminology Criteria for Adverse Events v 4.0 (CTCAE v 4.0).

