### 8.4 Rationale for Dose and Regimen

A single agent Phase I study in advanced cancer (N=74) determined the recommended Phase II dose for the Schedule 3/1 (3 weeks on and 1 week off, cycling) and Schedule 2/1 (2 weeks on and 1 week off, cycling) to be 125 mg/d and 200 mg/d, respectively. Two additional studies using the Schedule 3/1 are ongoing at Pfizer. For this study, Schedule 3/1 will be utilized unless adverse events require dose modifications as described below (**Table 8.1**).

**Table 8.1** Dose Modification Levels for PD0332991

Dose Level	Daily oral dose	Number of tablets	
		100 mg	25 mg
	per day x 21d, 1 w off		
Standard Dose	125 mg	1	1
Dose Reduced – 1	100 mg	1	0
Dose Reduced – 2	75 mg	0	3

**Table 8.1** outlines the recommended dose reductions for bone marrow toxicity due to PD-0332991.

Study eligible subjects potentially may have baseline myelosuppression due to their underlying liver disease or hypersplenism that is equivalent, according CTCAE v 4 scale to Grade 1 leucopenia, neutropenia and thrombocytopenia and Grade 2 anemia. For example, subjects are eligible to be enrolled on this study with:

- Hemoglobin  $\geq$  8.0 g/dl (CTCAE v 4 Grade 2)
- WBC  $\geq$  4,000/uL (CTCAE v 4 Grade 1)
- Absolute neutrophil count  $\geq$  1,500/uL (CTCAE v 4 Grade 1)
- Platelets  $\geq$  75,000/uL ((CTCAE v 4 Grade 1)

See **Table 8.2** for definitions and **4.1 Eligibility Inclusion Criteria**.

**Table 8.2** Standard CTCAE v 4 scale

Adverse Event	0	1	2	3	4
Hemoglobin (Hgb)	WNL	< LLN - 10.0 g/dl	8 - < 10 g/dl	6.5 - < 8 g/dl	< 6.5 g/dl or life threatening
WBC	WNL	< LLN - 3.0 x 10  /L	$\geq$ 2.0 - < 3.0 x 10  /L	$\geq$ 1.0 - < 2.0 x 10  /L	< 1.0 x 10  /L
ANC	WNL	< LLN – 1.5 x 10  /L	$\geq$ 1.0 - < 1.5 x 10  /L	$\geq$ 0.5 - < 1.0 x 10  /L	< 0.5 x 10  /L
Platelets	WNL	< LLN - 75 x 10  /L	$\geq$ 50.0 - < 75.0 x 10  /L	$\geq$ 25 - < 50.0 x 10  /L	< 25 x 10  /L

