If a subject is not able to tolerate the 75 mg dose, then treatment should be discontinued. If a dose reduction has been performed, the subject may be re-escalated by the treating physician provided toxicities have resolved to Grade 2.

**Table 8.3** outlines the procedures for dose modifications for bone marrow toxicity related to PD0332991.

Due to baseline coagulopathy and tendency to have bleeding events due to underlying liver disease, dose modifications should not be based on hemoglobin values. If a subject experiences bone marrow toxicity of both WBCs and platelets the recommended dose adjustment should be based on WBC count. It is recommended that standard of care be followed for administration of RBCs and platelets and for vitamin K in patients with ESLD.

**Table 8.3** Dose modifications/delays for bone marrow toxicity related to PD0332991

Grade of Event CTCAE v 4.03	Dose Interruption	Dose Modification for Remainder of Cycle.	Dose Modification for Subsequent Cycles
0-2	Treat on time	No change	No change
3-4	
 
• Delay until <math>\leq</math> Grade 2
 
• Administer 6 mg pegfilgrastim (Neulasta) subcut if WBC/ANC does not recover to <math>\leq</math> Grade 2 after 1 week dose interruption
 
	
 
• First episode: No change
 
• Second episode within cycle after co-administration with pegfilgrastim: Reduce 1 dose level
 
	
 
• Continue at dose level from previous cycle
 
• If serious drug-related myelosuppression occurs including: A. febrile neutropenia or B. sepsis with neutropenia, in previous cycle institute permanent dose reduction at -1 dose level
 
• If bone marrow toxicity recurs at <math>\geq</math> Grade 3 with leucocyte growth factor administration then
 

			institute permanent dose reduction at -1 dose level 
 
• If unable to resume PD-0332991 due to BM toxicity for an entire cycle, institute permanent dose reduction at -1 dose level
 
• If bone marrow toxicity remains at <math>\leq</math> Grade 2 for remainder of a previous cycle after administration of pegfilgrastim, then administer with subsequent cycles, 6 mg subcut on day 1 once per cycle
 

--	--	--	---

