### **9.13 Non-Hematological and Hematological Adverse Events**

Patients will be assessed clinically for toxicity prior to each dose using the National Cancer Institute (NCI) CTCAE Version 4. If patients experience Grade 3 or greater toxicity deemed related to study drug, PD-0332991 will be temporarily discontinued. After the resolution of toxicity to Grade 1 or less, PD-0332991 will be restarted at the initial dose. The study treatment will be continued until disease progression or unacceptable side effects (Grade 3 or greater). Patients with unacceptable side effects (Grade 3 or greater) for a second time on PD-0332991 will be removed from the study. The only exception to this are: Grade 3 anorexia, nausea vomiting, stomatitis/mucositis or diarrhea that will lead to investigational product withdrawal only if not manageable despite maximum supportive care. Throughout the study investigators may prescribe any concomitant medications or treatments necessary to provide adequate supportive care other than experimental or approved anti-tumor therapies. All concomitant medications must be recorded.

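### For related Grade 3-4 WBC, ANC or platelet toxicity, sections 5.3 and 9.13 contradict Table 8.3 and section 8.4 on the second event and on restart, and no visible clause says which governs

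*Combined protocol and SAP*

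**What the plan says.** Two parts of the combined protocol and SAP tell the investigator what to do about Grade 3 or worse toxicity judged related to study drug.

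**General rules.** Section 5.3 holds drug and then states: "After the resolution of toxicity to Grade 2 or less, PD-0332991 will be restarted at the initial dose". Section 9.13 repeats the rule with a different recovery grade: "After the resolution of toxicity to Grade 1 or less, PD-0332991 will be restarted at the initial dose". Both then remove the subject at a second event. Section 5.3 reads: "Subjects with unacceptable side effects (Grade 3 or greater) for a second time on PD-0332991 will be removed from the study". Section 9.13 reads: "Patients with unacceptable side effects (Grade 3 or greater) for a second time on PD-0332991 will be removed from the study". The carve-out, in the same terms in both, begins: "The only exception to this are: Grade 3 anorexia, nausea vomiting, stomatitis/mucositis or diarrhea". Bone marrow toxicity is not in it.

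**Marrow rules.** Section 8.4 gives dose levels of 125, 100 and 75 mg. It says that Table 8.1 "outlines the recommended dose reductions for bone marrow toxicity due to PD-0332991". Table 8.3 delays drug at Grade 3-4 until Grade 2 or less and leaves the dose unchanged for a first episode. It cuts one level at a second episode in the cycle once pegfilgrastim has been given. In later cycles it keeps the previous dose unless a listed trigger calls for a permanent reduction. Section 8.4 adds: "If a subject is not able to tolerate the 75 mg dose, then treatment should be discontinued". It also says that hemoglobin should not drive dose changes.

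**Other relevant text.** Section 5.4 leaves it to the investigator's "clinical judgment to determine whether an adverse event is related and of sufficient severity to require" removal. Section 5.6 item 3 withdraws subjects for unacceptable toxicity. Section 9.10 refers the reader to Section 8.1 for the hematologic interruption rules.

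**The concern.** Myelosuppression is the drug's principal dose-limiting toxicity (section 1.2), and all eleven dose-limiting toxicities reported from phase I were neutropenia and/or thrombocytopenia (section 9.10). These rules are therefore likely to be used. At a second related Grade 3-4 neutropenia, one part of the protocol takes the subject off study and another keeps the subject on treatment. An investigator cannot follow both.

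The first stake is safety and consistent care: when drug restarts, at what dose, and when it stops for good. The second is a possible knock-on to efficacy. Section 11.1 limits its analysis population to subjects with at least two cycles and a week 8 assessment, and replaces those who are not evaluable. Section 7.1 can date the TTP event at the last dose when disease could not be assessed. Which toxicity rule is followed could therefore change who is analysed and when an event is counted.

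**Working it through.** No planned figure is in dispute, so the check sets the texts side by side and adds simple arithmetic from Tables 8.1 to 8.3 and section 4.1.

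**1. Related Grade 3-4 WBC, ANC or platelet event**

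| Situation | 5.3 | 9.13 | Table 8.3 and 8.4 |
|---|---|---|---|
| Recovery needed to restart | Grade 2 or less | Grade 1 or less | Grade 2 or less |
| Uncomplicated first episode | initial dose | initial dose | no change (agrees) |
| Second episode | remove | remove | continue or reduce |
| Whole cycle missed | initial dose | initial dose | permanent cut to level -1 |
| Febrile neutropenia or neutropenic sepsis | initial dose | initial dose | level -1 from the next cycle |

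The last row is a conflict only when the restart falls in the next cycle.

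**2. Which Table 8.3 reduction steps survive 5.3 and 9.13?** There are four triggers.
- Second episode in the cycle after pegfilgrastim: needs a second event, so the subject has already been removed.
- Recurrence at Grade 3 or more despite growth factor: the same.
- Whole cycle missed: contradicts restart at the initial dose.
- Serious myelosuppression in the previous cycle: contradicts it when restart falls in the next cycle.

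So 2 of 4 cannot be reached, 1 of 4 conflicts directly and 1 of 4 conflicts conditionally. Going from 125 to 100 to 75 mg takes two reductions. If one event lowers the dose by at most one level (an assumption), 75 mg needs two events. Sections 5.3 and 9.13 keep a subject on study after only one, so 75 mg is never used for these toxicities.

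**3. Size of the recovery-grade difference.** Lower limits from Table 8.2 and entry limits from section 4.1, in x10^9/L:

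| | Grade 2 limit | Grade 1 limit | Entry limit | Grade 2 / entry | Grade 1 / entry |
|---|---|---|---|---|---|
| ANC | 1.0 | 1.5 | 1.5 | 1.0/1.5 = 67% | 1.5/1.5 = 100% |
| Platelets | 50 | 75 | 75 | 50/75 = 67% | 75/75 = 100% |
| WBC | 2.0 | 3.0 | 4.0 | 2.0/4.0 = 50% | 3.0/4.0 = 75% |

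A subject who enrolled at the ANC or platelet limit must return fully to the entry value under 9.13, but only to two thirds of it under 5.3 and Table 8.3.

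**4. Anemia.** Entry allows hemoglobin of 8 g/dL, which is Grade 2. After related Grade 3 anemia, recovery to Grade 1 under 9.13 means at least 10 g/dL, which is 2 g/dL above the entry floor. Because 8.4 keeps hemoglobin out of dose modification, Table 8.3 supplies no replacement rule.

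**5. Does any clause settle precedence?** None in the text available. Section 8.1, where 9.10 points, is a drug description with no hematologic parameters. Part of section 8.4, between Table 8.2 and the 75 mg rule, was not available to check.

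**6. Route to the endpoint.** Section 5.4 schedules toxicity checks every two weeks, so weeks 2, 4 and 6 precede the week 8 scan and a second event by then is feasible. Maximum accrual of 25 less 19 evaluable leaves 6 replacements. The documents give no rate of second Grade 3-4 marrow events at 125 mg, so no number of affected subjects is projected.

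**The case against.** The best defence is that the specific rule governs the general one. Table 8.3 is titled for related marrow toxicity, 8.4 makes the schedule subject to the modifications it sets out, and the faulty pointer in 9.10 probably means the section 8 hematologic rules (the table of contents misnumbers that section's parts too). The trial has one site, the Sponsor-Investigator must approve dose adjustments, and a medical monitor reviews events. This makes precedence for Table 8.3 a reasonable reading and limits inconsistent handling. But the heading of 9.13 names hematological events, its exceptions are stated to be the only ones, and both general sections equate unacceptable side effects with Grade 3 or greater. Oversight says who decides, not which rule applies.

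Several stronger readings are tempting and are not supported:
- A reader might infer that the rules clash at every marrow event. For an uncomplicated first episode the dose rules agree.
- A reader might extend the conflict with Table 8.3 to anemia. Section 8.4 takes hemoglobin out of dose modification.
- A reader might take failure at 75 mg as the sole ground for stopping. Section 5.6 adds investigator judgment, unacceptable toxicity, and under 50% of the required dose for two consecutive cycles. The 75 mg level is 75/125 = 60%, so it does not trigger that last rule by itself.
- A reader might infer, from the 8.4 sentence that bases adjustment on WBC when WBC and platelets are both affected, that drug could be given despite Grade 3-4 platelets. That sentence concerns dose adjustment. Table 8.3 puts interruption in a separate column, so the platelet hold stands.
- A reader might infer that TTP will be distorted. Events in phase I were described as reversible and generally not a cause of discontinuation. Toxicity removal is not among the reasons in 5.4 for ending imaging. A long hold under Table 8.3 could also leave a subject short of two cycles, and 11.1 also says efficacy is estimated for all subjects.

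**Conclusion.** The inconsistency is real and should be fixed. It is limited to related Grade 3-4 WBC, ANC and platelet toxicity: opposite actions at a second event, different restart doses in two further situations, and a recovery grade in 9.13 that is one grade stricter than in 5.3 and Table 8.3. Anemia is a linked gap that any repair has to cover. Consequences for the 11.1 analysis set and for TTP are possible and unquantified.

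Confidence is moderate. The conclusion assumes that the unavailable part of 8.4 contains no governing clause. The statement that 75 mg cannot be reached also assumes at most one dose level per event.

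**What to change.** 1. Add to 5.3 and 9.13: *For related Grade 3-4 WBC, ANC or platelet toxicity, Table 8.3 and section 8.4 govern hold, restart, dose level and the action at a second event; such an event managed under Table 8.3 is not by itself unacceptable toxicity under 5.6 item 3.*
2. State the rule for related Grade 3-4 anemia separately. Either keep the hold and removal rules of 5.3 and 9.13, or say that it is managed by transfusion without dose change, as 8.4 implies. If the hold is kept, set recovery at Grade 2 or less, since entry permits Grade 2.
3. In 9.13, set recovery for these marrow events to Grade 2 or less. For all other toxicities, choose one grade and use it in both 5.3 and 9.13.
4. Correct the pointer in 9.10 to Table 8.3.

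If the sponsor prefers removal at a second marrow event, say so in 8.4 and delete the reduction steps that then cannot be reached. The phase I experience summarised in 9.10 favours keeping Table 8.3.

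The cost is a short protocol amendment. The clinical downside is that some subjects restart at lower counts than 9.13 now allows (for example platelets of 50 rather than 75 x10^9/L) and stay on treatment after a second marrow event.

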## **10. Concomitant Medications and Non-Drug Therapies**

All subjects will be asked to provide a complete list of all prescription and over the counter medications. The investigator must be informed of any new medication(s) as soon as possible for the time of screening to the completion of follow-up.

### **10.1 Permitted medications**

All concomitant medications taken during the study will be recorded in the CRF with indication, dose, and dates of administration. Subjects should receive full supportive care during the study including transfusion with blood and blood products, antibiotics, recombinant human granulocyte colony stimulating factor or erythropoiesis-stimulating agents, bisphosphonates when appropriate. Anti-emetics may be administered prophylactically or in the event of nausea. Anti-diarrheals may be administered as needed for diarrhea.

### **10.2 Permitted medications- use with caution**

Analgesics such as acetaminophen and nonsteroidal anti-inflammatory medications should be administered with caution or not at all in subjects with impaired liver function. The use of heparin or low molecular weight heparin should be cautioned against in patients with HCC and cirrhosis, however may be indicated in specific situations. Due to dual potential for severe bleeding warfarin should not be administered.

### **10.3 Drug Interactions**

Formal drug-drug interaction studies have not been conducted with PD-0332991. Pre-clinical data indicate that PD-0332991 is metabolized *in vivo* primarily via the cytochrome P-450 enzyme, CYP3A4. Therefore concomitant use of certain medications (substrates of CYP3A4 should be undertaken with **caution** due to potential for alterations in the pharmacological effects of these medications or an increased risk for serious or life threatening adverse events. Furthermore, there may be a risk of drug-drug interactions. These medications include but are not limited to: ergot derivatives - dihydroergotamine, ergonovine, ergotamine, methylergonovine (potential for developing ergot toxicity including vasospasm leading to peripheral neuropathy and cerebral ischemia); neuroleptics - pimozide (potential increased risk for QT prolongation, ventricular arrhythmia and sudden death); antiarrhythmics - bepridil, flecainide, lidocaine, mexiletine, amiodarone, quinidine, propafenadone (potential increased risk for QT prolongation

and Torsades de Pointes); immune modulators - cyclosporine, tacrolimus, sirolimus (potential increased risk for nephrotoxicity and neurotoxicity; and miscellaneous drugs - quetiapine, risperidone, clozapine and atomoxetine. Concomitant administration of agents known to induce or inhibit CYP3A isoenzymes may increase plasma drug concentrations of PD-0332991. Selection of alternative concomitant medications with no potential to inhibit CYP3A4 is recommended. Medications which may induce CYP3A4 and may decrease plasma concentrations of PD-0332991 are glucocorticoids - high dose cortisone or hydrocortisone, prednisone, methylprednisolone and dexamethasone; anticonvulsants - phenytoin, carbamazepine, phenobarbital, oxcarbazepine; HIV antivirals - efavirenz, nevirapine;; antibiotics- rifampin, rifabutin, rifapentene and miscellaneous medications - St. John's Wort, modafinil, pioglitazone, troglitazone, omeprazole, verapamil. Primidone. PROHIBITED during the study are the strong CYP3A4 inhibitors which includes but are not limited to antibiotics- erythromycin, clarithromycin, telithromycin, troleandomycin; HIV protease inhibitors- ritonavir, indinavir, nelfinavir, saquinavir, amprenavir, lopinavir, delaviridine; antifungals- itraconazole, ketoconazole, voriconazole, fluconazole; antidepressants- nefazodone and grapefruit juice.

### **11.0 Statistical Considerations**

This is Phase II open-label non-randomized single institution study with an anticipated 12-24 month accrual. The size of the study is based on biostatistical modeling of HCC and is powered to demonstrate an improved TTP. The sample size calculation is based on historical data, which demonstrates that median TTP for untreated patients with HCC is 12 weeks, and median TTP for patients treated with Sorafenib is 24 weeks (Llovet et al. 2008, Cheng et al. 2009). The proposed study will test whether PD-0332991 treatment results in at least a 24 week TTP versus the historical median of 12 weeks. For a trial with an alpha of 0.05 and power of 90%, a sample size of 19 evaluable patients is needed.

### **11.1 Evaluation of Efficacy**

Efficacy endpoints will be estimated for all subjects. The tumor response endpoints will be performed on all subjects. The population will be evaluated on an intent-to-treat analysis defined as subjects who received at least two cycles of study medication and have completed the week 8 response assessments. TTP, ORR will be assessed by standard imaging (MRI and/or CT scans, as appropriate) utilizing modified RECIST (Version 1.1) criteria. Assessments will be performed at screening and after every 2 cycles of treatment (every 8 weeks) thereafter. TTP and overall survival will be evaluated using the Kaplan-Meier method. Median TTP and median survival will be estimated with corresponding 90% confidence intervals. Subjects that are not evaluable will be replaced with subjects with evaluable data.

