### **3.0 Study Design**

This is an open-label non-randomized single-institution study for subjects with inoperable, recurrent/refractory advanced hepatocellular carcinoma (HCC). Subjects must have failed or be intolerant of standard first line therapy, sorafenib (Nexavar®). Eligible subjects will receive 125 mg PD-0332991 capsules orally once daily, administered days 1-21 of a 28-day cycle, in repeated cycles.

Subjects will be permitted to receive protocol directed therapy until disease progression by modified RECIST (Version 1.1) (Response Evaluation Criteria in Solid Tumors) guidelines or clinical progression, unacceptable toxicity, withdrawal of consent or death. Tumor response assessment will be performed by the Investigator and will consist of evaluation by CT or MRI using modified RECIST (Version 1.1) guidelines every 8 weeks. Subjects who discontinue therapy for disease progression or other reasons will be followed for safety on Day 28 ( $\pm$  3 days), Day 56 ( $\pm$  3 days) and every 3 months thereafter or until death, from the last administration of protocol –directed therapy.

Subjects will be continuously assessed for evidence of acute and cumulative toxicity. Vital signs, Physical examinations, performance status, laboratory safety tests will be obtained and assessed prior to drug administration and at regular intervals throughout the study. Toxicity will be evaluated every 2 weeks during the first 3 cycles and thereafter monthly (once per cycle) by the Investigator according to National Cancer Institute (NCI) Common Terminology Criteria for Adverse Events (CTCAE), Version 4.0 (which can be viewed on-line at the following NCI web site: <http://ctep.cancer.gov/reporting/ctc.html>).

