## 7.0 Endpoints:

### 7.1 Primary Endpoint

#### Time to Progression (TTP)

Progression-free survival (PFS) is the time elapsed between treatment initiation and tumor progression or death from any cause, with censoring of patients lost to follow up. Time to

Progression (TTP) is defined by the FDA as the time from subject randomization until tumor progression is documented. Time to treatment failure (TTF) is a composite endpoint defined as the time from randomization until the patient stops trial treatment for any reason including progression, adverse events, insufficient therapeutic response, death, failure to return, and refused treatment/did not cooperate/withdrew consent. PFS assumes that patient deaths are randomly related to tumor progression. Compared to TTP, PFS is the preferred regulatory endpoint however in situations where deaths may be unrelated to cancer such as in patients with HCC and cirrhosis, TTP is an acceptable endpoint. In this study, TTP will be defined as the date of enrollment on trial to the first observation of disease progression, as classified by modified RECIST (Version 1.1) or clinical progression. The date of last dose of treatment or death will be used as the date of this event in the case that recurrent disease was not assessable. An interim analysis for futility will be conducted after the first 10 events have occurred. The probability of a significant final result given the observed data at the time of the interim analysis (i.e., the conditional power) will be estimated (Lachin 2005). The study will be stopped for futility if the conditional power is less than 60%. That is, the study will be stopped if there is a preponderance of evidence that completion will not yield a significant result.

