### **Overall Response Rate**

The best overall response is the best response recorded from the start of treatment until disease progression or recurrence. The objective response rate (ORR) is the proportion of subjects with either a confirmed CR or a confirmed PR as determined using modified RECIST (Version 1.1) criteria, as evaluated by the Investigator. A confirmed CR or PR requires repeat assessments no less than 28 days after the response criteria are first met. Subjects who have not met this criteria for response will be considered non-responders. As the clinical relevance of stable disease (SD) may be important in HCC, subjects with the response of SD will be recorded and documented. Disease control rate defined as CR + PR +SD will be calculated for all subjects treated with PD-0332991.

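### The set labelled intent-to-treat requires two cycles and a completed week-8 assessment, contradicts the plan's own all-subjects and TTP event rules, and can bias median TTP upward

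*Combined protocol and SAP*

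**What the plan says.** Section 11.1 (Evaluation of Efficacy) gives two populations. It opens with "Efficacy endpoints will be estimated for all subjects" and "The tumor response endpoints will be performed on all subjects". It then specifies an "intent-to-treat analysis defined as subjects who received at least two cycles of study medication and have completed the week 8 response assessments", and closes with "Subjects that are not evaluable will be replaced with subjects with evaluable data". The term evaluable has no separate definition. Section 11.0 says "a sample size of 19 evaluable patients is needed", and the Protocol Summary caps accrual at 25.

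Section 7.1 starts TTP at enrollment and counts both modified-RECIST progression and clinical progression. Where disease could not be assessed, it adds: "The date of last dose of treatment or death will be used as the date of this event". Section 7.2 (Overall Response Rate) says "Subjects who have not met this criteria for response will be considered non-responders", and calculates the disease control rate over all treated patients. Under section 3.0, treatment continues until progression by the modified RECIST "guidelines or clinical progression, unacceptable toxicity, withdrawal of consent or death". Section 5.4 sets imaging every 8 weeks, so the first scheduled on-treatment scan is at week 8.

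**The concern.** A patient must stay on treatment and be scanned at about week 8 to enter the restricted set, so membership depends on the outcome being measured. The patients left out can include those who fail earliest. The 12-week benchmark in section 11.0 is stated without any such condition, and a single-arm trial has no control group in which the same exclusion would cancel.

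The primary result can therefore differ according to which sentence the analyst follows, and under the restricted set an inactive drug can look active. The response rate and overall survival would be affected too, but only if they are analysed on that set. For response, section 7.2 points to an all-treated denominator.

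**Working it through.** **1. The plan's own figure.** Section 11.0 gives medians of 24 versus 12 weeks, alpha 0.05 and power 90%. Sidedness and test are not stated. For a one-sample exponential comparison, events = (z_alpha + z_beta)² / (ln 2)².
- One-sided: (1.645 + 1.282)² / 0.4805 = 17.8, so 18 events. Power with 19 events is 91.6%.
- Two-sided: 21.9, so 22 events. Power with 19 events is 85.6%.

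The 19 is thus reproduced, within one patient, on a one-sided reading, which also fits the 90% confidence intervals in section 11.1. It presumes that nearly every analysed patient has an event.

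**2. The rules side by side.** Take a patient who progresses clinically or dies at week 5.
- Section 7.1: a TTP event at week 5 (for the death, where disease was not assessable).
- Section 11.1, opening sentences: included.
- Section 11.1, restricted definition: excluded and, on the only available reading of not evaluable, replaceable.
- Section 7.2: a non-responder. On the restricted set, the same patient is missing from the denominator.

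**3. Shift in the median.** Assume exponential TTP with a true median of 12 weeks. The share failing before week 8 is 1 − 2^(−8/12) = 0.370. Let f be the fraction of these early failures removed; the documents do not give it. The retained share is K = 1 − 0.370f, and the retained median solves 2^(−m/12) = K/2, so m = 12·log2(2/K).

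**4. False-positive rate.** Simulation, 40,000 runs: enroll until 19 patients are evaluable or 25 are enrolled, then reject 12 weeks if 2·ΣT·ln 2/12 exceeds the 95th percentile of chi-square on 2n degrees of freedom. In the scan rows, progression is dated at the next multiple of 8 weeks. The early failures that the restricted set would remove keep their true dates when everyone is kept.

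| f | 0.25 | 0.50 | 0.75 | 1.00 |
|---|---|---|---|---|
| K | 0.907 | 0.815 | 0.722 | 0.630 |
| Retained median (weeks) | 13.7 | 15.5 | 17.6 | 20.0 |
| Continuous times, restricted set | 0.09 | 0.17 | 0.29 | 0.49 |
| Continuous times, first 19 all kept | 0.05 | 0.05 | 0.05 | 0.05 |
| 8-weekly scans, restricted set | 0.35 | 0.51 | 0.69 | 0.85 |
| 8-weekly scans, first 19 all kept | 0.21 | 0.19 | 0.17 | 0.15 |
| Chance of 19 evaluable within 25 | 0.99 | 0.84 | 0.44 | 0.13 |

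With scans and nobody removed the rate is already 0.24. That is a separate scan-interval effect; the gap between the two scan rows is what the exclusion adds.

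**5. A case tied to the plan's limits.** 25 − 19 = 6, and 6/25 = 24%. If all 24% were early failures, f = 0.24/0.370 = 0.65, K = 0.76 and m = 12·log2(2/0.76) = 16.8 weeks. In 60,000 runs the false-positive rate is 0.23 (continuous) or 0.62 (scans), against 0.05 and 0.18 with the first 19 all kept.

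**6. A second test.** Use an exact binomial test on the number of patients past 12 weeks (reject at 14 or more of 19, exact alpha 0.032) with continuous times. The restricted set gives 0.08/0.20/0.42/0.72 across the four values of f, against about 0.03 with all kept.

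**The case against.** The strongest reply is that the opening sentences of section 11.1, together with section 7.2, already support an all-subjects analysis, under which this bias does not arise. Since not evaluable is undefined, reading the replacement rule as covering everyone outside the week-8 set is an inference. This stands as far as it goes. But on that reading the restricted definition and the replacement rule have no clear function, and the sample size is still set in evaluable patients. That the text supports both readings is itself the defect.

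On size, four points have force:
- **Futility stop.** The rates above leave out the section 7.1 stop at 10 events when conditional power is below 60%. Adding it lowers the continuous-time restricted-set rates to about 0.05/0.09/0.18/0.33 if conditional power uses the current trend, or 0.08/0.15/0.27/0.45 under the 24-week alternative. The plan does not say which applies. The all-kept rate falls too, to about 0.03 or 0.045, so the direction and roughly the relative inflation survive.
- **High removal fractions are unlikely.** Radiological progression first seen on the week-8 scan stays in the set, and eligibility requires a life expectancy above 3 months.
- **Scan-dated rates mix two effects.** They also assume that the 12-week benchmark is true time; the documents do not say how it was measured.
- **Toxicity and withdrawal stops are not always early TTP failures.** Removing stops unrelated to progression would not raise the median. Conversely, counting them at last dose when disease is not assessable moves TTP toward time to treatment failure and could lower it. That follows from the plan's own section 7.1 rule, but it should be acknowledged.

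**Conclusion.** The concern holds and must be fixed. The plan gives incompatible rules for who counts in its primary analysis and does not rank them. If the restricted set governs and early failures are removed, median TTP is biased upward.

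The size is illustrative. It rests on exponential TTP, an assumed one-sided 5% test that the plan does not name, and a removal fraction that the documents do not give. Even the smallest fraction tabulated, one quarter, moves a true 12-week median to 13.7 weeks and nearly doubles the continuous-time false-positive rate before any futility stop. The figures at 100% are an upper bound. The target of 19 is not itself in error on the one-sided reading.

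**What to change.** In section 11.1, name one primary TTP population: all enrolled patients who received at least one dose. Measure TTP from enrollment, score early failures by the section 7.1 rule, and allow no replacement in the primary analysis. State that the response rate uses the same all-treated denominator, consistent with the non-responder rule in section 7.2, and name the overall-survival population. Restate the target of 19 evaluable patients and the cap of 25 in section 11.0 and the Protocol Summary to match. Draw the 10 events for the interim look from the same population.

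Keep the two-cycle, week-8 set only as a secondary evaluable analysis, without the intent-to-treat label, and report how many patients it leaves out and why. Because the section 7.1 rule can count toxicity or withdrawal stops as events, also report how many TTP events arose that way.

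The cost is wording in sections 11.0 and 11.1 and the Protocol Summary. No new procedures are needed, and accrual need not exceed 25. With 19 events among patients kept regardless of outcome, the continuous-time model gives about 5% one-sided error and about 91.5% power at 24 weeks. The reported median TTP and response rate may be less favourable. The change removes the exclusion bias but not the upward shift from 8-weekly scans, so it should not be described as restoring exactly 5%.
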